I 12. Capable of giving signed informed consent as described in [Section 10.1](#) (Appendix 1) which includes compliance with the requirements and restrictions listed in the informed consent form (ICF) and in this protocol. In countries where legal age of adulthood is above 18 years, a specific ICF must also be signed by the participant's legally authorized representative.

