 - Other biologics: within 5 half-lives (if known) or 16 weeks prior to baseline visit, whichever is longer
- E 19. Treatment with an investigational drug within 8 weeks or within 5 half-lives (if known), whichever is longer, prior to baseline
- E 20. Regular use (more than 2 visits per week) of a tanning booth/parlor within 4 weeks of the screening visit
- E 21. Planned or anticipated use of any prohibited medications and procedures (see [Section 6.5](#))
- E 22. Treatment with live (attenuated) vaccine within 12 weeks before the screening visit

Prior/concurrent clinical study experience

- E 23. Current participation in another investigational clinical study

Diagnostic assessments

- E 24. Not applicable.

Other exclusions

- E 25. Any other condition (medical, personal, familial, social, environmental, etc.) as assessed by the Investigator, that could significantly alter sleep parameters and confound study assessments
- E 26. Planned or anticipated major surgical procedure during the patient's participation in this study
- E 27. Pregnant or breast-feeding women, or were planning to become pregnant or breastfeed during the patient's participation in this study
- E 28. Women unwilling to use adequate birth control, if of reproductive potential* and sexually active. Adequate birth control is defined as agreement to consistently practice an effective

and accepted method of contraception throughout the duration of the study and for at least 12 weeks after last dose of study drug. These include hormonal contraceptives, intrauterine device, or double barrier contraception (ie, condom + diaphragm) or a male partner with documented vasectomy. Additional requirements for acceptable contraception may apply in certain countries, based on local regulations. Investigators in these countries will be notified accordingly in a protocol clarification letter

*For females, menopause is defined as at least 12 consecutive months without menses; if in question, a follicle stimulating hormone (FSH) level of ≥ 25 mU/mL must be documented. Hysterectomy, bilateral oophorectomy, or bilateral tubal ligation must be documented, as applicable; if documented, women with these conditions are not required to use additional contraception.

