10.2 APPENDIX 2: CLINICAL LABORATORY TESTS

- Urine human chorionic gonadotropin pregnancy test (as needed for women of childbearing potential) will be performed by the local laboratory.
- The local laboratory results used to make a study intervention decision or response evaluation must be entered into the CRF.
- Protocol-specific requirements for inclusion or exclusion of participants are detailed in [Section 5](#) of the protocol.
- Additional tests may be performed at any time during the study as determined necessary by the Investigator or required by local regulations.

Investigators must document their review of each laboratory safety report.

Laboratory/analyte results that could unblind the study will not be reported to investigative sites or other blinded personnel until the study has been unblinded.

10.3 APPENDIX 3: ADVERSE EVENTS: DEFINITIONS AND PROCEDURES FOR RECORDING, EVALUATING, FOLLOW-UP, AND REPORTING

DEFINITION OF AE

AE definition

- An AE is any untoward medical occurrence in a patient or clinical study participant, temporally associated with the use of study intervention, whether or not considered related to the study intervention.
- Note: An AE can therefore be any unfavorable and unintended sign (including an abnormal laboratory finding), symptom, or disease (new or exacerbated) temporally associated with the use of study intervention.

Events meeting the AE definition

- Any abnormal laboratory test results (hematology, clinical chemistry, or urinalysis) or other safety assessments (eg, electrocardiogram [ECG], radiological scans, vital signs measurements), including those that worsen from baseline, considered clinically significant in the medical and scientific judgment of the Investigator (ie, not related to progression of underlying disease).
- Exacerbation of a chronic or intermittent pre-existing condition including either an increase in frequency and/or intensity of the condition.
- New conditions detected or diagnosed after study intervention administration even though it may have been present before the start of the study.
- Signs, symptoms, or the clinical sequelae of a suspected drug-drug interaction.
- Signs, symptoms, or the clinical sequelae of a suspected overdose of either study intervention or a concomitant medication.

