10.4 APPENDIX 4: CONTRACEPTIVE GUIDANCE AND COLLECTION OF PREGNANCY INFORMATION

DEFINITIONS:

Woman of childbearing potential (WOCBP)

A woman is considered fertile following menarche and until becoming postmenopausal unless permanently sterile (see below).

Women in the following categories are not considered WOCBP

1. Premenarchal
2. Premenopausal female with 1 of the following:
 - Documented hysterectomy
 - Documented bilateral salpingectomy
 - Documented bilateral oophorectomy

Note: Documentation can come from the site personnel's: review of the participant's medical records, medical examination, or medical history interview.

3. Postmenopausal female
 - A postmenopausal state is defined as no menses for 12 months without an alternative medical cause. A high FSH level in the postmenopausal range may be used to confirm

a postmenopausal state in women not using hormonal contraception or hormonal replacement therapy (HRT). However, in the absence of 12 months of amenorrhea, a single FSH measurement is insufficient.

- Females on HRT and whose menopausal status is in doubt will be required to use 1 of the non-estrogen hormonal highly effective contraception methods if they wish to continue their HRT during the study. Otherwise, they must discontinue HRT to allow confirmation of postmenopausal status before study enrollment.

CONTRACEPTION GUIDANCE

Female participants

Female participants of childbearing potential are eligible to participate if they agree to use a highly effective method of contraception consistently and correctly as described in [Table 6](#).

In addition, WOCBP must refrain from donating ova for the duration of the study and for 12 weeks after the last dose of study intervention.

Table 6 - Highly effective contraceptive methods

Highly effective contraceptive methods that are user dependent^a Failure rate of <1% per year when used consistently and correctly.
Combined (estrogen and progestogen containing) hormonal contraception associated with inhibition of ovulation ^b 
• Oral• Intravaginal• Transdermal
Progestogen only hormonal contraception associated with inhibition of ovulation 
• Oral• Injectable
Highly effective methods that are user independent^a

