Implantable progestogen only hormonal contraception associated with inhibition of ovulation ^b 
• Intrauterine device (IUD)• Intrauterine hormone-releasing system (IUS)• Bilateral tubal occlusion
Vasectomized partner A vasectomized partner is a highly effective contraception method provided that the partner is the sole male sexual partner of the WOCBP and the absence of sperm has been confirmed. If not, an additional highly effective method of contraception should be used.

Sexual abstinence

Sexual abstinence is considered a highly effective method only if defined as refraining from heterosexual intercourse during the entire period of risk associated with the study intervention. The reliability of sexual abstinence needs to be evaluated in relation to the duration of the study and the preferred and usual lifestyle of the participant.

NOTES:

- a Typical use failure rates may differ from those when used consistently and correctly. Use should be consistent with local regulations regarding the use of contraceptive methods for participants participating in clinical studies.
 - b Hormonal contraception may be susceptible to interaction with the study intervention, which may reduce the efficacy of the contraceptive method. In this case, 2 highly effective methods of contraception should be utilized during the intervention period and for at least [X, corresponding to time needed to eliminate study intervention plus 30 days for study interventions with genotoxic potential] after the last dose of study intervention.
-

PREGNANCY TESTING:

- WOCBP should only be included after a confirmed menstrual period and a negative highly sensitive urine pregnancy test.
- Standard urine pregnancy testing will be performed for WOCBP participants throughout the study (see study SOA [Section 1.3](#)).
- Pregnancy testing will also be performed whenever a menstrual cycle is missed or when pregnancy is otherwise suspected.

COLLECTION OF PREGNANCY INFORMATION:

Male participants with partners who become pregnant

- The Investigator will attempt to collect pregnancy information on any male participant's female partner who becomes pregnant while the male participant is in this study. This applies only to male participants who receive study intervention.

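### E 28 accepts condom plus diaphragm as adequate birth control, but Appendix 4 ties eligibility to Table 6, which lists no barrier method, and no text says which rule governs

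*Protocol*

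**What the plan says.** **Protocol 5.2, E 28** excludes sexually active women of reproductive potential who are unwilling to use adequate birth control. It asks for consistent use of an effective and accepted method during the study and "for at least 12 weeks after last dose of study drug". On methods it says: "These include hormonal contraceptives, intrauterine device, or double barrier contraception (ie, condom + diaphragm) or a male partner with documented vasectomy". A proviso allows further requirements in certain countries, notified to investigators there by clarification letter. E 28 does not mention Appendix 4 or Table 6.

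**Protocol 10.4, Appendix 4**, under contraception guidance, says: "Female participants of childbearing potential are eligible to participate if they agree to use a highly effective method of contraception consistently and correctly", and points to Table 6 for the methods. Table 6 covers combined and progestogen-only hormonal methods, implant, intrauterine device, hormone-releasing intrauterine system, tubal occlusion, vasectomised partner and abstinence. Its user-dependent section carries a failure-rate heading of below 1% per year. Vasectomy counts "provided that the partner is the sole male sexual partner of the WOCBP and the absence of sperm has been confirmed". The table continues: "If not, an additional highly effective method of contraception should be used".

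**Protocol 5.1, I 12** makes consent include "compliance with the requirements and restrictions listed in the informed consent form (ICF) and in this protocol". The opening of Protocol Section 5 rules out waivers of enrolment criteria. Appendix 6, on country-specific requirements, is marked not applicable.

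**The concern.** Both texts are worded as eligibility rules, and they give different answers for the same woman. A site screening from E 28 could enrol a participant who uses condom plus diaphragm, while a site that also applies Appendix 4 would not. With waivers ruled out, the same enrolment could be acceptable at one site and a deviation at another; SAP 5.2 counts randomising an ineligible patient as a randomisation irregularity.

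What is at stake is a uniform level of protection against pregnancy during exposure to study drug and in the weeks after it.

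**Working it through.** The point rests on no sample size, power or alpha figure, so the check is a side-by-side reading with simple counts.

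**1. Methods named in E 28.** Hormonal, intrauterine device, double barrier, partner vasectomy: 4. The list is introduced as inclusive, not exhaustive, and the standard is an effective method rather than a highly effective one.

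**2. Entries in Table 6.**
- Combined hormonal (oral, intravaginal, transdermal): 3
- Progestogen-only (oral, injectable): 2
- Implant: 1
- Intrauterine device: 1
- Hormone-releasing intrauterine system: 1
- Tubal occlusion: 1
- Vasectomised partner: 1
- Abstinence: 1

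Total 3 + 2 + 1 + 1 + 1 + 1 + 1 + 1 = 11. Barrier methods among them: 0.

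**3. Each E 28 method against Table 6.**

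| E 28 method | In Table 6? | Difference |
|---|---|---|
| Double barrier | No | Not excluded by E 28; does not meet Appendix 4 |
| Hormonal, unqualified | In part | Combined, progestogen-only and implant entries must inhibit ovulation |
| Partner vasectomy, documented | Yes | Two added conditions: only male partner; absence of sperm confirmed. Otherwise a further highly effective method |
| Intrauterine device | Yes | None |

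Double barrier is wholly absent from Table 6. Hormonal methods are accepted more widely in E 28. Vasectomy is accepted in both places, with more detail in Table 6.

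**4. Does other text settle it?** The E 28 proviso covers only certain countries, while the Appendix 4 sentence has no country limit. Appendix 6 adds nothing. I 12 points towards applying both texts but does not rank them. The SAP does not address contraceptive methods.

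**5. Safeguards.** Appendix 4 says: "WOCBP should only be included after a confirmed menstrual period and a negative highly sensitive urine pregnancy test". The schedule of activities (Protocol 1.3) has urine tests at screening, baseline and weeks 4, 8, 12, 16, 20 and 24, which is 2 + 6 = 8, and marks them for unscheduled visits. Testing is also done after a missed cycle or on suspicion, and study drug stops if a participant becomes pregnant (Protocol 8.3 and Appendix 4).

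**6. Limit of those safeguards.** The last injection is planned at week 22, so the contraception period runs to at least week 22 + 12 = 34. The last scheduled test is at week 24. For about 34 − 24 = 10 weeks there is no scheduled test, and the method itself is the main protection.

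**The case against.** The best reply is that the rules do not strictly contradict each other. E 28 is an exclusion criterion and Appendix 4 adds a further condition. A woman can satisfy both, and read together the stricter text applies. I 12 and the bar on waivers support that reading. On vasectomy, Table 6 can fairly be taken as spelling out what E 28 leaves short. This largely stands. What remains is that a site must infer the cumulative reading, because no supplied text states it.

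Some stronger readings are tempting, but the documents do not carry them.

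- **Table 6 is the intended standard and E 28 is simply wrong.** Table 6 note b still holds an unfilled placeholder, and Appendix 4 lists premenarchal status in an adult trial. Both look like template text. Amendment 1, by contrast, edited the E 28 contraception period to match the investigator's brochure and consent form. Either text could be the intended one.
- **Section 5 overrides the appendix.** Appendix 2 does say "Protocol-specific requirements for inclusion or exclusion of participants are detailed in" Section 5, but that bullet sits among the laboratory-test notes and gives Section 5 no precedence over Appendix 4.
- **The note b placeholder should read 12 weeks.** Note b applies only if study drug interferes with hormonal contraception, and nothing supplied says that it does.
- **Sites have in fact applied different standards.** The consent form and any country letters were not supplied, so divergence is possible but not shown.

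**Conclusion.** The inconsistency is real and stands in current protocol text. Its core is double barrier: named in E 28 and absent from all 11 Table 6 entries. The unqualified acceptance of hormonal methods in E 28 is a second, narrower mismatch, so double barrier should not be described as the only one. The vasectomy conditions are a difference of detail.

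The documents give no basis for the number of women affected, and the testing and stopping rules limit the consequence. Testing detects pregnancy but does not prevent it. The correction is worth making because it is cheap and bears on participant protection. There is no effect on power, type I error or the primary analysis. The conclusion assumes that no unseen document, such as the consent form or a clarification letter, already states a single standard.

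**What to change.** State one contraception standard and use it in both places.

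- **Simplest version, in line with the cumulative reading:** have E 28 require a method listed in Table 6, with that table's conditions, and delete double barrier from E 28.
- **If the sponsor intends E 28 to govern:** amend the Appendix 4 eligibility sentence and Table 6 to match it.

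The cost is wording in the next amendment and a clarification letter to sites. Under the first version, a few women may need to change or add a method, or may fail screening.

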5.3 LIFESTYLE CONSIDERATIONS

Not applicable.

5.4 SCREEN FAILURES

Screen failures are defined as participants who consent to participate in the clinical study but are not subsequently eligible to be enrolled in the study. A minimal set of screen failure information is required to ensure transparent reporting of screen failure participants to meet the Consolidated Standards of Reporting Trials publishing requirements and to respond to queries from regulatory authorities. Minimal information includes demography, screen failure details, eligibility criteria, and any AE.

Individuals who do not meet the criteria for participation in this study (screen failure) may be re-screened, typically once.

6 STUDY INTERVENTION

Study intervention is defined as any investigational interventions, marketed products, placebo, or medical devices intended to be administered to a study participant according to the study protocol.

6.1 STUDY INTERVENTION(S) ADMINISTERED

Table 2 - Overview of study interventions administered

Study intervention name	Dupilumab	Placebo
Dosage formulation	Dupilumab 300 mg for SC administration is supplied as 150 mg/mL solution in 2.25 mL pre-filled glass syringes to deliver 300 mg in 2.0 mL	Placebo for dupilumab will be provided in identically matched glass pre-filled syringe to deliver 2 mL, which will match dupilumab 300 mg.
Unit dose strength(s)/Dosage level(s)	300 mg	Not applicable
Route of administration	Subcutaneous	Subcutaneous
Dosing instructions	Dupilumab 300 mg SC Q2W (with a 600 mg loading dose at randomization Day 1, then followed with dupilumab 300 mg SC Q2W until week 10); At week 12, dupilumab 300 mg plus 1 placebo to mask prior blinding; then followed with 300 mg SC Q2W with a last injection at week 22	Placebo SC Q2W to deliver 2 mL (with placebo loading dose at randomization Day 1, then followed with 1 placebo dose Q2W until week 10); At week 12, dupilumab 600 mg loading dose; then followed with dupilumab 300 mg SC q2w with a last injection at week 22
Packaging and labeling	Dupilumab will be supplied as 1 glass pre-filled syringe packed in a patient kit box. Both glass pre-filled syringe and box will be labeled as required per country requirement.	Placebo will be supplied as 1 glass pre-filled syringe packed in a patient kit box. Both glass pre-filled syringe and box will be labeled as required per country requirement.

Abbreviations: SC=subcutaneous; Q2W=every 2 weeks

INVESTIGATIONAL MEDICINAL PRODUCT(S)

Investigational medicinal product (IMP) will be administered by the Investigator/health care professional or designee following clinic procedures and blood collection. Patients should be monitored by site personnel or by caregiver[s] (if at home) for at least 30 minutes after administration of all IMP injections.

Subcutaneous injection sites should alternate between the upper thighs, 4 quadrants of the abdomen or the upper arms, so that the same site is not injected twice during consecutive visits.

At on-site study visit(s) during the treatment period, patients or their caregivers will be trained by the investigator or delegate on how to prepare and self-inject/inject the IMP, until they are proficient and feel comfortable to self-inject/inject the IMP at home for certain intervals per

Section 1.3. This training must be documented in the patient's study file. At baseline visit, the Investigator or delegate will perform the first of the 2 injections, and will propose to the patient or his/her caregiver to perform the second injection under the supervision of the investigator or delegate. If a patient or caregiver does not feel comfortable to self-inject/inject the IMP, all injections can be done on-site or, as an alternative, they can be done by a healthcare professional (nurse) at patients' home, after an appropriate and documented training.

Patient or caregiver injection should only be performed in the abdomen or upper thighs. Patient should also be instructed to monitor for any reaction for at least 30 minutes (or longer per country-specific or local site-specific requirements) following injection.

For doses not given at the study site, diaries will be provided to record information related to the injections. The diary will be kept as source data in the patient's study file.

Between the protocol-scheduled on-site visits, interim visits may be required for IMP dispensing. As an alternative to these visits, IMP may be supplied from the site to the participant via a Sponsor-approved courier company where allowed by local regulations and approved by the subject.

NONINVESTIGATIONAL MEDICINAL PRODUCT(S)

Patients will receive standardized background treatment (ie, non-investigational medical products [NIMP]) consisting of TCS as noted below. Between the protocol-scheduled on-site visits, interim visits may be required for NIMP dispensing. As an alternative to these visits, TCS may be supplied from the site to the participant via a Sponsor-approved courier company where allowed by local regulations and approved by the subject.

Starting on Day -7, all patients are required to undergo treatment with medium-potency TCS using a standardized regimen according to the following guidelines:

- Apply medium-potency TCS, 1 fingertip unit for each 2% BSA, once daily to areas with active lesions. Low-potency TCS or TCI may be used on areas that cannot be treated safely with medium-potency TCS (eg, face, neck, intertriginous, and genital areas, areas of skin atrophy, etc.)
- When lesions are under control, apply topical medication twice weekly; resume daily applications when lesions reactivate
- Monitor the patient for signs of local or systemic TCS toxicity and stop/adjust treatment as necessary

Typical TCS products to be used as standardized background treatment include triamcinolone acetonide 0.1% cream or fluocinolone acetonide 0.025% ointment for medium-potency, and hydrocortisone 1% cream for low-potency. If patients have tolerance issues with any of these products or if they are not commercially available in some countries, they may substitute with products of the same potency from the list provided in the Study Reference Manual. On areas treated with TCS, moisturizers should be applied once daily only at the time when TCS is not applied (ie, do not use moisturizers and TCS on the same areas at the same time of the day). For

example, if TCS are applied in the evening, moisturizers will not be used in the evening on areas treated with TCS; however, will be applied to those areas in the morning. On areas not treated with TCS, moisturizers will be applied twice daily – morning and evening. The type, amount, and frequency of topical products used during the study will be recorded at home by patients in a medication log if possible, including the amount (number of fingertip units) used.

